8.5.1. Safety Monitoring Rules for Liver Chemistry Tests

The following rules are adapted from the draft guidance for industry, "Drug-Induced Liver Injury: Premarketing Clinical Evaluation," issued by the U.S. Department of Health and Human Services, Food and Drug Administration, July 2009. For a definition of Baseline, please refer to guidance in Section 8.5 above.

In the event of an ALT or AST measurement that is $> 3 \times ULN$ at any time during the study (Treatment or Post-Treatment Period), the initial measurement(s) should be confirmed as described above. Additional, confirmatory measurements should also be performed if ALT or AST levels increase to $5 \times ULN$.

Frequency of Repeat Measurements: Patients with confirmed ALT or AST levels $> 3 \times ULN$ should have their liver chemistry tests (ALT, AST, ALP, INR and total bilirubin) retested at least once-weekly until ALT and AST levels become $\le 1.2 \times ULN$ or $1.2 \times baseline$ value if the baseline value was > ULN.

Further Investigation into Liver Chemistry Elevations: For patients with confirmed ALT or AST levels $> 3 \times ULN$, the following evaluations should be performed:

- Obtain a more detailed history of symptoms and prior and concurrent diseases
- Obtain further history for concomitant drug use (including nonprescription medications, herbal and dietary supplement preparations), alcohol use, recreational drug use, and special diets
- Obtain a history for exposure to environmental chemical agents and travel

- Serology for viral hepatitis (hepatitis A virus [HAV] immunoglobulin M [IgM], HBsAg, HCV antibody, cytomegalovirus [CMV] IgM, and EBV antibody panel)
- Serology for autoimmune hepatitis (e.g., antinuclear antibody [ANA], smooth muscle antibody IgG, Liver-Kidney Microsome-1 Antibody, IgG)

Additional liver evaluations, including gastroenterology/hepatology consultations, hepatic computed tomography (CT), or magnetic resonance imaging (MRI) scans, may be performed at the discretion of the Investigator, in consultation with the Sponsor Medical Monitor. Repetition of the above evaluations should be considered if a patient's ALT and/or AST levels reach $5 \times ULN$.

For a definition of Baseline, please refer to guidance in Section 8.5.

8.5.2. Safety Monitoring Rules for Platelet Count Results

Please refer also to Table 5.

Platelet count will be monitored every 2 weeks during the Treatment Period and at the following visits in the Post-Treatment Period: Study Days 85, 92, 106, 120, 148, and 169. The Investigator should review all platelet count results within 48 hours of receipt. If a patient's platelet count falls to 100,000/mm³ or less, then the patient's platelet counts should be monitored as described in Table 5. In case of platelet reduction to < 50,000/mm³, the platelet monitoring rule defined in Stopping rules (Section 8.6.3) should be followed.

Treatment should be held if there is no evaluable platelet count within 18 days prior to the scheduled dose. Any uninterpretable platelet count result must be rechecked and determined not to have met a stopping rule before dosing can continue. If Day 1 results are uninterpretable, Day 8 dosing may proceed, however, an interpretable result is required (and must be reviewed) before study drug dosing on Day 15.

In the event of a platelet count < 75,000/mm³, additional laboratory investigations may be conducted after discussion between the Investigator and the Sponsor Medical Monitor including: fibrinogen or D-dimer (local lab), complement (total C3, total C4, C5a), peripheral smear, citrated sample for platelets, CBC with reticulocytes and mean platelet volume, coagulation panel (prothrombin time/international normalized ratio [PT/INR], activated partial thromboplastin time [aPTT]), total globulins [IgG and IgM]), serology for hepatitis B virus, HCV, HIV (if not done at Screening), anti-platelet antibodies (specialty lab), and anti-drug antibodies (specialty lab).

Any case of a platelet count < 50,000/mm³ should be reported to the Sponsor in an expedited fashion (see Section 9.3.4). The Study Medical Monitor will discuss the assessment and treatment of such subjects with the Investigator.

Table 5: Monitoring Schedule and Stopping Rules for Platelet Counts

Platelet Count on Rx	Drug Dose	Monitoring
> 100,000/mm ³	No action	Monitor per Schedule of Procedures (Appendix A)
$\geq 75,000-$ $\leq 100,000/\text{mm}^3$	No action	Monitor every week until 3 successive values > 100,000/mm ³
≥ 50,000– < 75,000/mm ³	Pause dosing When platelet count returns to > 100,000/mm³ restart dosing only if approved by Sponsor Medical Monitor	Monitor at least twice weekly until 3 successive values > 75,000/mm³ then weekly until 3 values > 100,000/mm³ If not redosing then subsequent monitoring should be per the Schedule of Procedures (Appendix A)
		If redosing then continue to monitor weekly for the remainder of the Treatment Period Consider discontinuation of antiplatelet agents / non-steroidal anti-inflammatory drug (NSAIDS) / anticoagulant medication while platelet count < 75,000/mm ³
≥ 25,000– < 50,000/mm ³	Permanently discontinue Study Drug	Report to the Sponsor in an expedited fashion Monitor at least twice weekly until 3 successive values > 75,000/mm³ then weekly until 3 values > 100,000/mm³. Subsequent monitoring should be per the Schedule of Procedures (Appendix A) Discontinue antiplatelet agents / NSAIDS / anticoagulant medication while platelet count < 75,000/mm³ if possible
< 25,000/mm ³	Permanently discontinue Study Drug	Report to the Sponsor in an expedited fashion Monitor daily until 3 successive values > 25,000/mm³ then monitor at least twice weekly until 3 successive values > 75,000/mm³ then weekly until 3 values > 100,000/mm³. Subsequent monitoring should be per the Schedule of Procedures (Appendix A) Corticosteroids recommended* Consider need for hospitalization and referral to hematologist Discontinue antiplatelet agents / NSAIDS / anticoagulant medication while platelet count < 75,000/mm³ if possible

^{*} Recovery in platelet count may be accelerated by administration of high-dose glucocorticoids. Treatment as recommended by the American Society of Hematology (ASH) (2019) guidelines for immune thrombocytopenia (Blood Advances, 10 DECEMBER 2019, Volume 3, Number 23) includes initial therapy with either dexamethasone 40 mg per day for 4 days, or prednisone 0.5 to 2.0 mg/kg per day. Prednisolone or prednisone may be administered for up to 2 to 4 weeks with taper; alternatively, intravenous immunoglobulin (IVIG) may be administered at 0.4 g/kg/d for 5 days, or infusions of 1 g/kg/d for 1-2 days (Provan et al. 2010; Provan et al. 2019).

8.5.3. Safety Monitoring for Minor Bleeding Events

Minor bleeding events are those that do not fulfill the criteria for major bleeding (MB) or clinically relevant, non-major bleeding (CRNMB) events (which are defined in Section 8.6.4), for example excess bruising, petechiae, gingival bleeding on brushing teeth. Additional testing of platelet counts and coagulation parameters (PT/INR/aPTT) should be considered after consultation with the Sponsor Medical Monitor.

8.5.4. Safety Monitoring for Potassium

In the event of a potassium measurement > 5.3 mmol/L at any time during the study (Treatment or Post-Treatment Period), the initial measurement(s) should be confirmed. If the initial potassium measurement is confirmed to be > 5.3 mmol/L, weekly monitoring will be initiated until levels return to < 5.3 mmol/L.

In the event of a potassium measurement ≥ 5.5 mmol/L, but less than 6.0 mmol/L, study drug is to be held. In the event of a potassium measurement ≥ 6.0 mmol/L refer to Section 8.6.5 Stopping Rule for Potassium. In the event of a potassium measurement ≥ 5.5 mmol/L, the Investigator or designee should assess for symptoms consistent with hyperkalemia (e.g., muscle weakness or paralysis). An ECG may be considered per Investigator judgement to assess electrocardiographic signs of hyperkalemia (delayed conduction, heart block, arrhythmias) which, if conducted, should be discussed with the Sponsor Medical Monitor or designee to determine continued dosing with Study Drug. The investigator or designee should consider treating the patients with therapies that reduce the serum potassium, such as a low-potassium diet, diuretics, or a reduction or cessation of medications that can increase the serum potassium (ACEi/ARB). Serum potassium should be measured frequently until documented to be < 5.5 mmol/L. Dosing with Study Drug may continue after a confirmed potassium measurement < 5.5 mmol/L with Investigator and Sponsor Medical Monitor or designee consultation.

8.5.5. Safety Monitoring for Blood Pressure

If the patient is symptomatic (i.e., dizziness, light-headedness, clammy skin, fatigue, blurry vision), at any point in the study, the patient should contact the Study Center immediately or should a patient experience a BP measurement of ≤ 90 mmHg (systolic) 2 additional measurements must be done within a 30-minute period. If the confirmed average of the 2 additional SBP measurements is ≤ 90 mmHg and/or the patient remains symptomatic, dosing of a patient with Study Drug will be paused. Oral and/or IV hydration should be instituted. The suitability of the patient for continued dosing will be determined by the Investigator in consultation with the Sponsor Medical Monitor after the SBP has normalized and/or patient is no longer symptomatic and will be based on the reversibility of initiating factors (e.g., decreased oral intake, cold/flu, other illness). If the patient remains symptomatic or if the SBP does not normalize Study Drug should be permanently discontinued (refer to Section 8.6.6).

8.6. Stopping Rules

For the purposes of the stopping rules, Baseline is defined as:

- Temporary stopping rules for renal function tests Baseline is defined as the average of the pre-dose test closest to Day 1 and Day 1
- Stopping rules for platelets Baseline is defined as the last non-missing measurement prior to the first dose

8.6.1. Stopping Rules for Liver Chemistry Elevations

In the event of laboratory results meeting the following criteria, and the event is without an alternative explanation as discussed with the Sponsor Medical Monitor, dosing of a patient with Study Drug (ISIS 757456 or placebo) will be stopped permanently; values that are not confirmed due to failure to retest or missing lab values will be presumed confirmed:

- 1. ALT or AST $> 8 \times ULN$, which is confirmed
- 2. ALT or AST > $5 \times ULN$, which is confirmed and persists for ≥ 2 weeks
- 3. ALT or AST $> 3 \times$ ULN, which is confirmed and total bilirubin $> 2 \times$ ULN or INR > 1.5
- 4. ALT or AST > 3 × ULN, which is confirmed, **and** the new appearance (i.e., onset coincides with the changes in hepatic enzymes) of fatigue, nausea, vomiting, right upper quadrant pain or tenderness, fever, rash, and/or concomitant eosinophilia (> ULN)

8.6.2. Stopping Rules for Renal Function Test Results

- 1. Confirmed 30% decline in eGFR from Baseline eGFR values [eGFR should be calculated using the CKD-EPI creatinine equation (Levey et al. 2009)]
- 2. Confirmed proteinuria: Absolute UPCR value ≥ 1000 mg/g

The possible dosing re-initiation or follow-up schedule for any events meeting either of these criteria will be determined by the Investigator **in consultation with** the Sponsor Medical Monitor or designee.

At the discretion of the Investigator, a decision to hold or permanently stop study drug may be made based on lesser changes in these parameters observed in isolation or in association with other renal-related abnormalities.

8.6.3. Stopping Rule for Platelet Count Results

See Table 5 for an overview of monitoring and stopping rules for platelet counts.

- In the event of a confirmed platelet count less than 50,000/mm³, dosing of a patient with Study Drug (ISIS 757456 or placebo) will be stopped permanently
 - The platelet count should be tested at least twice weekly until 3 successive values above 75,000/mm³
 - Then tested weekly until 3 values above 100,000/mm³
 - Subsequent monitoring should follow the Schedule of Procedures (Appendix A)

- In the event of any platelet count less than 25,000/mm³, dosing of the patient with Study Drug will be stopped permanently
 - Platelet count should be monitored daily until 3 successive values above 25,000/mm³
 - Then monitor at least twice weekly until 3 successive values above 75,000/mm³
 - Then monitor weekly until 3 successive values above 100,000/mm³
 - Then monitor per the Schedule of Procedures (Appendix A)
 - Administration of corticosteroids is recommended for patients whose platelet count is less than 25,000/mm³, with referral to a hematologist.

In the event of a platelet count $< 75,000 / \text{mm}^3$ and $\ge 50,000 / \text{mm}^3$, and in the absence of MB or CRNMB (defined below), dosing with Study Drug should be suspended temporarily until the platelet count has recovered to $> 100,000 / \text{mm}^3$. The suitability of the patient for continued dosing will be determined by the Investigator in consultation with the Study Medical Monitor and will be based on factors such as the original rate of decline in the patient's platelet count, whether any bleeding events were experienced, and the speed of recovery of platelet count after interruption of dosing. If dosing is reinitiated, platelet count must be measured twice weekly (consider more frequent monitoring if risk factors for bleeding are present) until 3 successive values above $75,000 / \text{mm}^3$ then weekly until the end of study. Treatment should be held if there is no evaluable platelet count within 18 days prior to the scheduled dose. Any uninterpretable platelet count result must be rechecked and determined not to have met a stopping rule before dosing can continue.

Labs to Be Performed in the Event of a Platelet Count Less than 50,000/mm³

The following is a list of recommended lab analyses for patients who have any occurrence of platelet count less than 50,000/mm³. Archived samples prior to Day 1 of investigational treatment may also be analyzed in order to determine the patient's baseline conditions.

Table 6: Recommended Laboratory Analyses

To Be Performed at Local Lab

Peripheral smear (should be performed locally, fixed, and sent to central lab for review)

Fibrinogen split products or D-dimer on fresh blood

To Be Performed at Central Lab

Citrated sample for platelets

Coagulation panel (PT/INR, aPTT)

CBC with reticulocytes

Total globulins: IgG and IgM

Complement: total C3, total C4, C5a

Serology for:

HBV, HCV, HIV (if not done recently for screening)

To Be Performed at Specialty Lab(s)

Antiplatelet antibodies

Anti-ASO antibody

Note: These labs may be performed in the event of a platelet count less than 75,000/mm³ after discussion with the Study Medical Monitor. Additional lab tests may be considered in order to ascertain potential causative conditions for significant platelet count decreases / thrombocytopenia.

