2.3.4. Clinical Experience

Detailed information concerning the clinical studies conducted with ISIS 757456 can be found in the Investigator's Brochure. A summary is included below.

The safety and tolerability of ISIS 757456 was evaluated in a total of 62 healthy volunteer subjects aged 18–60 in a blinded, placebo-controlled, Phase 1 study ISIS 757456-CS1. Of these 62 subjects, 46 received ISIS 757456 (29 in the single-dose cohorts and 17 in the multiple-dose cohorts), and 16 received placebo. ISIS 757456 was well-tolerated at doses up to 80 mg administered as a single dose and 480 mg total dose (80 mg administered as 6 doses over 6 weeks). ISIS 757456 demonstrated dose-dependent plasma reduction of AGT levels following multiple doses, and there were no dose-dependent clinically meaningful trends in laboratory assessments and no serious adverse events (SAE). The Phase 1 study did not result in hypotension, hyperkalemia or renal changes. The elimination half-life of ISIS 757456 was estimated to be approximately 2-4 weeks.

ISIS 757456-CS2 was a Phase 2 multicenter, double-blind, placebo-controlled study to assess the safety, tolerability and efficacy of ISIS 757456 in patients with controlled BP. The study enrolled 25 patients randomized 2:1 (ISIS 757456 to placebo) to receive 80 mg ISIS 757456 or placebo for 6 weeks. The patients were washed out of their antihypertensive medications prior to Study Day 1 and the BP was confirmed to be uncontrolled after washout. A 54% mean reduction of AGT was observed at an 80 mg weekly dose over 6 weeks. A trend in blood pressure lowering was observed in patients treated with ISIS 757456 compared to placebo. Mean systolic blood pressure was reduced 7.5 mmHg in patients treated with ISIS 757456 and 1.7 mmHg in placebo patients. No rebound hypertension was observed. ISIS 757456 was well-tolerated and there were no clinically meaningful trends in laboratory assessments, including hypotension and hyperkalemia, no adverse events of special interest (AESI), and no related SAEs (Morgan et al. In Press).

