3.4.3. Post-Treatment

Patients are to return to the Study Center for Post-Treatment visits on Study Days 85, 92, 106, 120, 148, and 169. The final study visit will be Study Day 169.

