6.1.2. Treatment Period

Eligible patients will be administered Study Drug (ISIS 757456 or placebo) on a weekly basis (12 weeks) for a total of 12 doses. Measurement and review of the in-clinic BP should be performed on the same day prior to administering the Study Drug. Of the 12 required study visits during the Treatment Period, 11 selected study visits have the option for Home Healthcare (a Sponsor approved vendor). Home Healthcare assessments and procedures may be conducted by a Home Healthcare professional at specified visits per the Schedule of Procedures (Appendix A) and as arranged by site staff. If 3 consecutive Home Healthcare visits have been conducted, the Sponsor must be consulted prior to the scheduling of a 4th in-home visit. The Home Healthcare visit must be conducted by a Home Healthcare professional that is appropriately trained prior to a Home Healthcare visit. If a visit cannot be performed in the clinic or by a Home Healthcare professional, patient contact (e.g., video call, text, email, etc.) is required by site personnel to assess any AEs, changes in concomitant medications, adequate hydration and low sodium diet counseling.

Safety and clinical laboratory evaluations as well as blood sampling for PK analysis will be performed periodically throughout the Treatment Period (Appendix A, Appendix B, and Appendix C). Any AEs and concomitant medications will be recorded. At each visit, qualified site staff will review vital signs and laboratory results prior to each dosing to ensure compliance with monitoring and stopping rules outlined in Section 8.

The patient is expected to maintain adequate hydration and a low sodium diet throughout the study. The study site will counsel and ask the patient at each in-clinic visit if (s)he is maintaining adequate hydration and a low sodium diet.

Patients who discontinue the Treatment Period early will continue in the study following the post-treatment evaluations (Section 6.1.3).

All safety data including AEs, BP, and concomitant medications will be reviewed by the Sponsor's Medical Monitor or designee on an ongoing basis throughout the trial

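### Table 5 and Section 8.6.3 set different platelet monitoring for patients restarted after a count of 50,000 to <75,000/mm³

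*Combined protocol and SAP*

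**What the plan says.** Two places in the protocol govern a count of 50,000 to <75,000/mm³.

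- **Section 8.5.2 and Table 5.** Section 8.5.2 says that counts of 100,000/mm³ or less are monitored by Table 5. It points to the 8.6.3 monitoring rule only below 50,000/mm³. The Table 5 row pauses dosing and allows restart above 100,000/mm³ with Sponsor Medical Monitor approval. During recovery it asks for counts at least twice weekly, then weekly. After restart: "If redosing then continue to monitor weekly for the remainder of the Treatment Period". The row names the Schedule of Procedures only for patients who are not redosed.
- **Section 8.6.3.** For the same band: "If dosing is reinitiated, platelet count must be measured twice weekly" until three counts in a row exceed 75,000/mm³, "then weekly until the end of study". This section also applies the temporary suspension only where there is no major bleeding (MB) or clinically relevant non-major bleeding (CRNMB). The Table 5 row has no such condition.

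The routine post-treatment platelet counts in Section 8.5.2 are on "Study Days 85, 92, 106, 120, 148, and 169". Section 3.4.3 adds: "The final study visit will be Study Day 169".

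**The concern.** The two rules cover the same patients and differ in how often and how long platelets are counted after restart. Section 8.6.3 is the stricter rule and is mandatory in tone, yet 8.5.2 directs sites with a patient in this band to the looser one.

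The difference falls mainly after dosing has ended. A restarted patient has already had a count below 75,000/mm³ on Study Drug, and the drug is cleared slowly (Section 2.3.4: "The elimination half-life of ISIS 757456 was estimated to be approximately 2-4 weeks"). The rule that holds treatment when no evaluable count exists within 18 days acts only on doses, so it gives no protection after the last one. From then on, scheduled counts are the routine safeguard.

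A smaller matter sits in the same row. A reader of Table 5 alone does not learn that 8.6.3 limits the pause-and-restart route to patients without MB or CRNMB.

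**Working it through.** The plan states no figure to reproduce. The check compares the two texts and counts the platelet tests each would give.

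**Frequency after restart**
- Table 5: weekly.
- Section 8.6.3: twice weekly until three counts in a row exceed 75,000/mm³, then weekly.
- If counts hold, the twice-weekly phase lasts about 3 / 2 = 1.5 weeks. This difference is short.

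**Duration after restart**
- Table 5: weekly counting is required to the end of the Treatment Period; nothing is stated for afterwards.
- Section 8.6.3: to the end of the study.

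**Counts after Day 85.** Assumptions: the patient's last visit, Day 169, is the end of study; the twice-weekly phase is over by Day 85; and, for Table 5, the patient returns to the 8.5.2 visit list after treatment.

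| | Section 8.6.3 | Table 5, then the 8.5.2 list |
|---|---|---|
| Days | 92, 99, ..., 169 | 92, 106, 120, 148, 169 |
| Number of counts | (169 − 92)/7 + 1 = 12 | 5 |
| Gaps from Day 85 (days) | 7 throughout | 7, 14, 14, 28, 21 |
| Longest gap (days) | 7 | 28 (Day 120 to Day 148) |

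Difference: 12 − 5 = 7 counts per restarted patient.

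**Bleeding condition.** Under Table 5 every patient in the band is paused, bleeding or not. Section 8.6.3 lists bleeding among the factors in the restart decision. The only open question is whether MB or CRNMB rules out restart:
- Section 8.5 names 8.6.1 to 8.6.6 as permanent-stop criteria. That range includes 8.6.4, which favours stopping.
- Section 8.6.4 contains only definitions, minor bleeding among them.
- Section 8.8 cites only 8.6.1 to 8.6.3 for laboratory stopping rules. It separately requires discontinuation for an adverse event that makes it necessary, which leaves a route by judgement.

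**The case against.** The best defence is that the texts are compatible. Table 5 does not forbid more frequent or longer counting, so a site that follows 8.6.3 also satisfies Table 5. Section 8.6.3 itself describes Table 5 as an overview, and Section 6.1.2 has staff review results before each dose "to ensure compliance with monitoring and stopping rules outlined in Section 8", not against one table. The frequency difference can also be partly reconciled by reading the twice-weekly recovery phase in Table 5 as running on across the restart.

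Some of this stands: the frequency difference is small, and a site reading both places can comply with both. But the label of overview does not explain a different duration. Section 8.5.2 makes Table 5 the working instruction for this band, and the review in 6.1.2 is tied to dosing, so it does not reach the post-treatment weeks.

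Three stronger readings are tempting and are not supported:

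- *A 49-day gap, from Day 120 to Day 169.* A reader might infer this because the Hematology row of Appendix A, as extracted, shows no mark at Day 148. Section 8.5.2 lists Day 148 expressly, and one blank cell in an extracted table may be an artefact. It is worth checking, but it should not be counted.
- *A quantified platelet risk from residual drug.* The half-life shows that exposure outlasts dosing. Nothing in the documents links a residual level to platelet decline.
- *Table 5 permits redosing after a serious bleed.* Restart still needs recovery above 100,000/mm³ and Medical Monitor approval, and bleeding is a listed factor. The texts leave the outcome unclear; they neither clearly permit restart nor clearly bar it.

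**Conclusion.** The inconsistency is real and minor. Two stated safety rules for the same patients differ, chiefly in how long weekly counting continues after restart. After Day 85 this amounts to 12 counts against 5, and a longest gap of 7 days against 28.

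Those figures rest on two readings. The first is that the end of study means the patient's own Day 169 visit; Section 3.5 defines End-of-Study for the whole trial as the last patient's last visit. The second is that a restarted patient under Table 5 returns to the visit schedule, which the row does not say.

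Few patients are likely to be affected. Screening excludes counts below 125,000/mm³, and the Synopsis reports that no platelet stopping rule was met in the two earlier Phase 2 trials. The documents give no rate for this band. No reading allows dosing while the count is in the band, and power and alpha are unchanged. The missing bleeding condition is a secondary ambiguity for the sponsor to settle.

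**What to change.** 1. In the Table 5 row for 50,000 to <75,000/mm³, replace the post-restart text with the 8.6.3 schedule: twice weekly until three successive counts exceed 75,000/mm³, then weekly through Day 169. Naming the day also removes the doubt about what end of study means.
2. Add to the same row the 8.6.3 condition that there is no MB or CRNMB. Have the sponsor confirm whether MB or CRNMB in this band means permanent discontinuation, and state the answer in both places. Do not resolve the mismatch by deleting the condition from 8.6.3.
3. Check that the Hematology row of Appendix A includes the Day 148 count that 8.5.2 lists.

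The cost is a wording change to one table row, a matching statement in 8.6.3 and, if needed, a clarification letter to sites. Compared with the visit schedule, a restarted patient has about 7 more post-treatment counts, all of which 8.6.3 already requires.
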